
standard deviation (SD), median, minimum, and maximum). Qualitative/categorical data will be summarized using frequencies and percentages.
 
The efficacy analyses will be conducted in the intent-to-treat (ITT) population using the last observation carried forward method to handle missing and incomplete efficacy data. The ITT population is defined as all randomized subjects. All data will be included and no subjects will be excluded because of protocol violations. The ITT population will be analyzed as randomized and will be used for the efficacy analyses. Sensitivity analysis on the primary endpoints will be performed on the Per Protocol (PP) population defined as all subjects who complete the study through Visit 7 (Day 17) without major protocol violations. The PP population will be analyzed as treated using observed data only.
 
Safety analyses will be conducted in the safety population defined as all randomized subjects who have received treatments. The safety population will be analyzed as treated.
  
Primary Efficacy Analysis: The primary efficacy endpoints are ocular itching assessed at Visit 4b and 5a (Duration and Onset of Action, respectively) at 5(±1), 7(±1), 10(±1) minutes post-CAC (0-4 scale, allowing half unit increments) and conjunctival redness evaluated by the Investigator at Visit 4b and 5a (for Duration and Onset of action, respectively) at 7(±1), 15(±1), and 20(±1) minutes post-CAC (0-4 scale, allowing half-unit increments). The average of each subject's eyes at each post-CAC time point will be used as the unit of analysis for both ocular itching and conjunctival redness. Ocular itching and conjunctival redness will each be analyzed using an analysis of covariance model for each post-CAC time point at these visits, with the time appropriate post-CAC scores at Visit 3 as a covariate and treatment group, including all four treatments, as the sole factor (least squared means will be used to compare each concentration of PRT-2761 to PV). Two-sample t-tests will be used as unadjusted sensitivity analyses at each post-CAC time point, as well as a non-parametric Wilcoxon rank sum tests (comparing each concentration of PRT-2761 to PV). At each post-CAC time point, treatment differences will be considered statistically significant for each primary endpoint if they are significant at a two-sided significance level of $\alpha = 0.05$.

Sponsor: Ora, Inc.
Name of Finished Product: PRT-2761 Ophthalmic Solution

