8.1.3 Criteria for Effectiveness

- To demonstrate efficacy for ocular itching, PRT-2761 in any concentration needs to show clinical superiority over PV by at least 0.5 units of a 5 point scale for all 3 post-CAC time points, 5(± 1), 7(± 1), 10(± 1) minutes post-CAC and at least [REDACTED] of the post-CAC time points.
- To demonstrate efficacy for conjunctival redness, PRT-2761 in any concentration needs to show clinical superiority over PV by at least 0.5 units of a 5 point scale for all 3 post-CAC time points, 7(± 1), 15(± 1), 20(± 1) minutes post-CAC [REDACTED] of the post-CAC time points.
- If ocular itching meets the efficacy measures as defined above with statistical significance, then the study will be considered a success for ocular itching.
- If conjunctival redness meets the efficacy measures as defined above with statistical significance, then the study will be considered a success for conjunctival redness.
- If both ocular itching and conjunctival redness meets the efficacy measures as defined above with statistical significance, then the study will be considered a success for both ocular itching and conjunctival redness.

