10.1.4 Procedures for Final Study Entry

Subjects must meet all of the inclusion criteria and none of the exclusion criteria prior to Visit 4a to be enrolled in the study.

10.1.5 Methods for Assignment to Treatment Groups:

All subjects screened for the study who sign an ICF will be assigned a 3-digit screening number that will be entered in the Screening and Enrollment Log. Screening numbers will be assigned in sequential order beginning with 001. Randomization will be used to avoid bias in the assignment of subjects to treatment and time point, to increase the likelihood that known and unknown subject attributes (e.g., demographics and baseline characteristics) are evenly balanced across treatment groups and across time points, and to enhance the validity of statistical comparisons.

Once a subject meets all qualification criteria at Visit 4a, they will be enrolled and randomly assigned to masked treatment using a 1:1:1:1 (PRT-2761 0.5%: PRT-2761 1%:PV:Patanol®) assignment ratio for the acute phase. Subjects randomized to the Patanol® treatment in the acute phase will further be randomized using a 1:1

(Patanol®:Pred forte®) assignment ratio for the chronic phase. Subjects will be randomized at Visit 4a (Day 1) by assignment of the lowest 4-digit randomization number available within the appropriate stratum. Randomization will be stratified by average post-CAC itching scores [REDACTED] at baseline (Visit 3), by qualifying allergen type (seasonal and perennial) and by confocal participation (yes and no) to ensure balance for the primary endpoint of ocular itching. The randomization numbers will start from x001, where x refers to the subject's stratum as follows:

[REDACTED]
[REDACTED]

The first 36 subjects who qualify after post-CAC assessments at Visit 3 and had tear collection at Visit 2, will be in the confocal microscopy subset. This number is estimated to ensure approximately 30 subjects in the confocal microscopy subset complete the trial. At Visit 4, these individuals will be assigned to a kit number from Stratum 5, 6, 7, or 8.

Once 36 subjects have completed confocal microscopy at Visit 3, any subjects who had tear collection at Visit 2, will not have additional tear collections or confocal microscopy. At Visit 4, these individuals will be assigned to a kit number from Stratum 1, 2, 3, or 4.

No randomization numbers will be skipped or omitted.

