12.11 PRIMARY EFFICACY ANALYSES

The primary efficacy endpoints are ocular itching assessed at 5(± 1), 7(± 1), 10(± 1) minutes post-CAC (0-4 scale, allowing half-unit increments) and conjunctival redness evaluated by the Investigator at 7(± 1), 15(± 1), 20(± 1) minutes post-CAC (0-4 scale, allowing half-unit increments) at Visit 4b (Duration of Action Visit) and 5a (Onset of Action Visit). The average of each subject's eyes at each post-CAC time point will be used as the unit of analysis for both ocular itching and conjunctival redness. Ocular itching and conjunctival redness will each be analyzed using an analysis of covariance (ANCOVA) model for each post-CAC time point at each visit, with the time appropriate post-CAC scores at Visit 3 as a covariate and treatment group (including all four treatments: PRT-2761 0.5%, PRT-2761 1%, PV, Patanol®), as the sole factor. Least square (LS) means will be used to compare each concentration of PRT-2761 to PV. Two-sample t-tests will be used as unadjusted sensitivity analyses at each post-CAC time point, as well as a non-parametric Wilcoxon rank sum tests (comparing each concentration of PRT-2761 to PV). At each post-CAC time point, treatment differences

Treatment success is defined as PRT-2761, for at least one concentration, showing clinical superiority over PV [REDACTED]
[REDACTED] 5(± 1), 7(± 1), 10(± 1) minutes post-CAC for ocular itching and 7(± 1), 15(± 1), 20(± 1) minutes post-CAC for conjunctival redness, a [REDACTED]
[REDACTED] of the post-CAC time points measured for both ocular itching and conjunctival redness.

The primary efficacy analyses will be conducted on the ITT population using the last observation carried forward method for missing data as described in [Section 12.4](#).
Sensitivity or supportive analyses will be performed on the ITT population using observed data only, [REDACTED]
[REDACTED]
[REDACTED]

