8.3 Definition of Baseline

For the primary efficacy variables (ocular itching and conjunctival redness), baseline will refer to the time point specific measure at Visit 3 (e.g., ocular itching at 5 minutes post-CAC at Visit 3 will be the baseline for ocular itching at 5 minutes post-CAC at Visits 4b, 5a, 5b, 6a, 6b, and 7).

Baseline for all secondary efficacy variables is defined in a manner similar to the baseline for the primary efficacy variables. For all safety variables, baseline is defined as the last measurement prior to the first dose of study medication.

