13.1 Primary Analysis

The primary efficacy endpoints are ocular itching assessed by the subject at 5(± 1), 7(± 1), 10(± 1) minutes post-CAC (0-4 scale, allowing half-unit increments) and conjunctival redness evaluated by the Investigator at 7(± 1), 15(± 1), 20(± 1) minutes post-CAC (0-4 scale, allowing half-unit increments) at Visit 4b (duration of action visit) and 5a (onset of action visit).

Ocular itching will be evaluated by the subject using the following Ora Calibra® CAC Ocular Itching Scale:

Conjunctival redness will be evaluated by the investigator using the following Ora Calibra® Ocular Hyperemia Scale (half unit increments are allowed):

The average of each subject's eyes at each post-CAC time point will be used as the unit of analysis for both ocular itching and conjunctival redness.

The primary efficacy analyses for ocular itching and conjunctival redness will be conducted on the ITT population with LOCF for missing data using analysis of covariance (ANCOVA) models. These statistical models will include treatment group (including all four treatments: PRT-2761 0.5%, PRT-2761 1%, Vehicle, Patanol®) and the time point specific post-CAC scores at Visit 3 as a measure of baseline. Least square (LS) means for each treatment, the estimated treatment differences and their corresponding 95% CI, and p-values will be calculated from these ANCOVA models and will be used to compare each concentration of PRT-2761 and Patanol® to Vehicle and each concentration of PRT-2761 to Patanol®.

[REDACTED]
[REDACTED]
[REDACTED]
[REDACTED]
[REDACTED]
[REDACTED]
[REDACTED]

To demonstrate efficacy for ocular itching, PRT-2761 in any concentration needs to show clinical superiority over vehicle by [REDACTED] post-CAC time points, 5(± 1), 7(± 1), 10(± 1) minutes post-CAC and at least 1 unit for the majority [REDACTED] of the post-CAC time points. The same criteria will be used to demonstrate efficacy for conjunctival redness.

If ocular itching meets the efficacy measures as defined above with statistical significance ([REDACTED]
[REDACTED]

[REDACTED] the study will be considered a success for ocular itching. Similarly, if conjunctival redness meets the efficacy measures as defined above with statistical significance, then the study will be considered a success for conjunctival redness.

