If both ocular itching and conjunctival redness meet the efficacy measures as defined above with statistical significance, then the study will be considered a success for both ocular itching and conjunctival redness.

Two-sample t-tests and non-parametric Wilcoxon rank sum tests will be used as unadjusted sensitivity analyses at each post-CAC time point. At each post-CAC time point, treatment differences will be considered statistically significant for each primary endpoint if they are significant at a two-sided significance level of $\alpha = 0.05$.

Sensitivity or supportive analyses will be performed on the following:

- ITT population with multiple imputation using MCMC methods for missing data;
- ITT population with BOCF for missing data;
- ITT population with observed data only;
- PP population with observed data only.

The number of subjects with itching scores less than one and with itching scores equal to zero will be summarized with counts and percentages by treatment group for each post-CAC time point at Visits 4b, 5a, 5b, 6a, 6b, and 7. For Visits 4b and 5a (acute phase), the number of subjects in each concentration of PRT-2761 and Patanol® will be compared to Vehicle and the number of subjects in each concentration of PRT-2761 will be compared to Patanol®. For Visits 5b, 6a, 6b, and 7 (chronic phase), the number of

subjects in each concentration of PRT-2761 and Patanol® will be compared to Pred forte® in addition to the treatment comparisons being made for the acute phase. A Fisher's exact test will be used to compare treatments for the number of subjects in each category and the corresponding p-values will be reported. Conjunctival redness scores will be summarized in a similar manner using categories of scores less than or equal to one and scores equal to zero.

Figures will be produced to show mean ocular itching score for each treatment arm by time point and visit (Visits 4b and 5a) for the ITT and PP populations with observed data only. Mean change from baseline of ocular itching scores for each treatment arm will be presented in a similar figure for the ITT population with observed data only. Mean conjunctival redness scores and mean change from baseline of conjunctival redness scores will also be presented in similar figures.

Separate listings of ocular itching scores and conjunctival redness scores for all subjects will also be provided.

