13.2 Secondary Analyses

Secondary endpoints include ocular itching; conjunctival, episcleral, and ciliary redness; chemosis; tearing/watery eyes; eyelid swelling; rhinorrhea; nasal pruritus; ear or palate pruritus; and nasal congestion. All secondary endpoints will be analyzed in a manner similar to the primary endpoints for the ITT population with observed data only and for the PP population with observed data only. The ANCOVA models used will include treatment group (including all five treatments: PRT-2761 0.5%, PRT-2761 1%, vehicle, Patanol®/Patanol®, Patanol®/Pred forte®) and the time point specific post-CAC scores at Visit 3 as a measure of baseline. For the acute phase (Part 1), LS means for each treatment, the estimated treatment differences and their corresponding 95% confidence intervals, and p-values will be used to compare each concentration of PRT-2761 and Patanol® to vehicle and each concentration of PRT-2761 to Patanol®. For the chronic phase (Part 2), LS means for each treatment, and the estimated treatment difference and their corresponding 95% confidence intervals, and p-values will be used to compare each concentration of PRT-2761, Patanol®/Patanol® and Patanol®/Pred forte® to vehicle. Each concentration of PRT-2761 will also be compared to Patanol®/Patanol® and Patanol®/Pred forte® separately.

In addition, repeated measures ANCOVA models will be run for each visit, with treatment, time point, and time appropriate baseline as covariates. These models account for correlations between time points within each subject. LS means for each treatment, the estimated treatment differences and their corresponding 95% confidence intervals (as described previously for each phase) will be calculated from these repeated measures ANCOVA models. SAS code to implement this repeated measures ANCOVA model for each visit is as follows:

The Kenward-Roger method will be used to determine denominator degrees of freedom. An unstructured variance-covariance matrix will be used for the above repeated measures model. If the model does not converge using the unstructured matrix, the first order autoregressive structure and the compound symmetry structure will be employed, in that order.

The secondary analysis variables will be presented in subject listings by visit and time point as appropriate.

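### The efficacy ANCOVAs leave out allergen type and confocal participation, which the randomisation stratifies on; if these are prognostic, the reported intervals are too wide

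*Protocol*

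**What the plan says.** Protocol 10.1.5 and SAP 4.1 stratify the randomisation on average Visit 3 post-challenge itching (low or high), and also "by qualifying allergen type (seasonal and perennial) and by confocal participation (yes and no) to ensure balance for the primary endpoint of ocular itching". SAP 4.1 lists the resulting eight strata.

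The primary model in the Protocol synopsis is an ANCOVA "with the time appropriate post-CAC scores at Visit 3 as a covariate and treatment group, including all four treatments, as the sole factor". Protocol 12.11 repeats it, with treatment "as the sole factor. Least square (LS) means will be used to compare each concentration of PRT-2761 to PV". SAP 13.1 agrees: "These statistical models will include treatment group (including all four treatments" and so on, together with the Visit 3 score at the same time point. The secondary ANCOVA in SAP 13.2 has the same form with five treatment groups. Its repeated-measures version is fitted "with treatment, time point, and time appropriate baseline as covariates".

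Under SAP 8.3, "baseline will refer to the time point specific measure at Visit 3" of the endpoint being analysed. An itching model therefore carries Visit 3 itching, and a redness model carries Visit 3 redness.

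In SAP 13.1, the list introduced by "Sensitivity or supportive analyses will be performed on the following" varies only the missing-data method or the population. The t-tests and Wilcoxon tests are described as unadjusted. SAP 16 summarises itching and redness separately by allergen type. SAP 10.1 tabulates all three stratification factors. SAP 18 declares no departures from the protocol analyses.

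**The concern.** Stratified allocation balances the chosen factors across arms, so their contribution to chance variation in the treatment difference is largely removed by design. An analysis that omits them does not see this. The between-stratum variation stays in the residual, the standard error is overstated, the confidence interval is too wide and the p-value too large.

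This happens only to the extent that the factors predict the outcome beyond the Visit 3 score already in the model. The treatment estimate stays unbiased, and the test is conservative rather than anti-conservative. What is at stake is the reported precision of every efficacy comparison, in a trial with 30 subjects per acute-phase arm and 15 in each active-control group in Part 2.

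**Working it through.** **The plan's own figure.** The planning SD, effect and power are not readable in Protocol 12.9 or SAP 5, so the power calculation cannot be reproduced. The visible arithmetic is consistent: 4 × 30 = 120 enrolled; 112 completers is 28 per arm, and 28 / (1 − 8/120) = 30; for the confocal subset, 30 / (1 − 6/36) = 36.

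**Inputs from the documents.** 30 per arm (Protocol 9.1.1), 36 of 120 in the confocal subset (Protocol 8.4), two-sided 5% level (SAP 8.4), and 0.5 units as the illustrative difference (Protocol 8.1.3).

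**Assumptions.** Residual SD σ of the planned model is 0.70 to 1.00. R², the share of that residual variance explained by the omitted factors, is 0 to 0.20. Allergen types split 50:50, and randomisation uses permuted blocks of 8.

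**Closed form, assuming perfect balance.**
- Reported SE, planned model: SE = σ√(2/30).
- Actual SE, which the adjusted model reports: SE × √(1 − R²). The ratio of planned to adjusted is 1/√(1 − R²).
- Actual type I error, planned model: 2{1 − Φ(1.96/√(1 − R²))}.
- Power, planned: Φ[(δ/SE − 1.96)/√(1 − R²)].
- Power, adjusted: Φ[δ/(SE√(1 − R²)) − 1.96].

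Example with σ = 0.80, δ = 0.5, R² = 0.10: SE = 0.80 × 0.2582 = 0.2066 and δ/SE = 2.421. Planned power is Φ[(2.421 − 1.960)/0.9487] = Φ(0.486) = 0.686. Adjusted power is Φ(2.421/0.9487 − 1.960) = Φ(0.592) = 0.723.

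| R² | SE ratio | Type I, planned | Equivalent extra subjects | Power, σ 0.80, planned / adjusted | Power, σ 1.00, planned / adjusted |
|---|---|---|---|---|---|
| 0 | 1.000 | 0.050 | 0% | 0.677 / 0.677 | 0.491 / 0.491 |
| 0.05 | 1.026 | 0.044 | 5% | 0.682 / 0.700 | 0.490 / 0.511 |
| 0.10 | 1.054 | 0.039 | 11% | 0.686 / 0.723 | 0.490 / 0.532 |
| 0.20 | 1.118 | 0.028 | 25% | 0.697 / 0.772 | 0.490 / 0.581 |

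**Simulation, itching-type model** (8,000 trials per setting, eight strata, σ = 0.85, R² split equally between the two factors). The adjusted model adds allergen type and confocal participation. Entries are planned / adjusted.

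| R² | Mean reported SE | Actual SD of the estimate | Rejection under the null | Power at 0.5 |
|---|---|---|---|---|
| 0 | 0.219 / 0.220 | 0.222 / 0.223 | 5.3 / 5.3% | 62.1 / 61.9% |
| 0.05 | 0.220 / 0.214 | 0.213 / 0.212 | 4.4 / 4.9% | 62.0 / 64.1% |
| 0.10 | 0.220 / 0.209 | 0.210 / 0.209 | 4.2 / 5.3% | 61.2 / 65.5% |
| 0.20 | 0.220 / 0.197 | 0.201 / 0.198 | 3.2 / 5.2% | 62.7 / 70.8% |

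The actual SD of the estimate barely differs between the models. The defect is that the planned model reports an SE larger than the actual one. Over σ = 0.70 to 1.00 the power loss is 1.4 to 2.2 points at R² = 0.05, 2.8 to 4.3 at 0.10, and 5.4 to about 9 at 0.20.

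**Simulation, redness-type model** (4,000 trials per setting, σ = 0.90, all three factors added). Power, planned vs adjusted, was 0.55 vs 0.55, 0.56 vs 0.58, 0.57 vs 0.62 and 0.57 vs 0.66 for R² = 0, 0.05, 0.10 and 0.20.

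**Success rule for one dose, endpoint and visit.** This requires "superiority over PV by at least 0.5 units of a 5 point scale for all 3 post-CAC time points" (Protocol 8.1.3) and at least 1 unit at the majority of them (SAP 13.1; taken here as two of three, with correlation 0.8 between time points). At a true difference of 1.0 and σ = 0.85, the planned and adjusted success rates were 49.9 vs 49.9%, 50.5 vs 50.7%, 48.7 vs 48.8% and 50.3 vs 50.2%. In every case they equalled the rate of meeting the point-estimate thresholds alone. At a true difference of 0.5 the rate is below 1% under either model.

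**The case against.** The strongest reply is that no decision changes. The estimate is unbiased, the error rate is controlled, and the success rule turns on point estimates. The 2, 4 and 8 point losses arise at a true difference of 0.5, where the success rule is almost never met. At a true difference of 1.0, single-time-point power is 99.6 vs 99.7% (σ = 0.85, R² = 0.10), and even at σ = 1.00 and R² = 0.20 it is 98.2 vs 99.0%. All of this stands, and it is why the point is minor.

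R² is also assumed. Confocal membership goes to the first qualifying subjects with adequate Visit 2 tears, which is largely logistic. Every subject is titrated and confirmed on one allergen, so the Visit 3 score may absorb much of any difference between allergen types. That is fair: R² = 0 is compatible with the documents, and nothing in them supports a value as high as 0.20. On the other side, the sponsor chose these factors in order to balance itching, and reports results by allergen type.

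Those by-allergen summaries do not answer the concern. They are separate displays and yield no adjusted overall estimate.

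Finally, text is redacted in Protocol 12.11 and 12.12 and in SAP 13.1, and the SAP 13.2 model code is not visible. A stratum-adjusted supportive analysis could sit there, so the statement is limited to the readable text. The wording that treatment is the only factor makes a hidden stratum term in the primary model unlikely.

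**Conclusion.** The point holds as a minor efficiency matter, with medium confidence. On the readable text, none of the efficacy ANCOVAs contains allergen type or confocal participation, and the non-itching models also lack the itching stratum. There is no bias and no inflation of type I error.

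The planned intervals are 0, 2.6, 5.4 or 12% wider than stratum-adjusted ones at R² of 0, 0.05, 0.10 or 0.20. At σ = 0.85, about 0, 2, 4 or 8 points of power are lost for a 0.5-unit difference at one time point. The success rule is not materially affected. The size depends on the assumed R² and residual SD, neither of which the documents give, and to a lesser degree on the assumed block size and allergen split.

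**What to change.** In Protocol 12.11 and SAP 13.1 and 13.2, add qualifying allergen type and confocal participation as main effects to the ANCOVA and repeated-measures models. For redness and the other non-itching endpoints, also add the low/high baseline-itching stratum. Main effects are preferable to eight stratum cells, some of which may be sparse. Keep the unadjusted t-tests and Wilcoxon tests as sensitivity analyses, and make the change before unmasking.

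The cost is one line per model. The primary ANCOVA has 120 − 5 = 115 residual degrees of freedom; the change leaves 113 for itching and 112 for redness. If the factors are not prognostic, the simulated loss of power is 0.1 to 0.4 points. The variables are already collected and tabulated (SAP 10.1).
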